1.3 SCHEDULE OF ACTIVITIES (SOA)

1.3.1 Screening

Study Visit	Screening (Day -2 to Day 1) ^a
Procedures	
Informed consent	x
Demographics	x
Medical history ^b	x
COVID-19 test (SARS-CoV-2 RT-PCR or antigenic test) ^c	x
Hepatitis B and C and HIV serology tests ^d	x
Review of inclusion and exclusion criteria	x
Collection of data related to current hospitalization ^e	x
Physical examination	x
cTnI level ^f	x
12-lead ECG ^g	x
Neurologic assessment	x
Glasgow Coma Scale (GCS) ^h	x
Bleeding assessment ⁱ	x
Adverse events	x
Prior medication	x
Pregnancy test (urine or blood) ^j	x
Platelet count and blood smear ^k	x
Serum creatinine ^k	x

Study Visit	Screening (Day -2 to Day 1) ^a
IxRS registration	x

Abbreviations: ADAMTS13 = a disintegrin-like and metalloprotease with thrombospondin repeats 13; COVID-19 = coronavirus disease 2019; CRF = case report form; cTnI = cardiac troponin I; ECG = electrocardiogram;

ICU = intensive care unit; IxRS = Interactive Voice/Web Response System; RT-PCR = reverse transcription polymerase chain reaction; TTP = thrombotic thrombocytopenic purpura.

- a The Screening Period should not exceed more than 2 days. Screening may also take place on the same day as the baseline (Day 1) visit. COVID test and pregnancy test results should be available before any baseline procedure on Day 1.
- b General medical history and TTP-specific medical history. The result of an ADAMTS13 activity test performed as per standard of care upon admission will be collected in the eCRF, if available.
- c Results of COVID-19 tests performed within 72 hours prior to ICF signing are acceptable.
- d Results of hepatitis B and C and HIV serology tests performed within 7 days of ICF signing are acceptable.
- e Hospitalization information will include information on admission and discharge from hospital and ICU and dates of symptom onset and diagnosis.
- f cTnI is the preferred assay. However, if this is not available, cTnT, high sensitivity cTnI or high sensitivity TnT are acceptable at Screening. Results of cTnI (or cTnT or high sensitivity cTnT or high sensitivity cTnT) tests performed within 24 hours prior to ICF signing are acceptable.
- g 12-lead ECG performed within 4 hours prior to ICF signing is acceptable.
- h To be assessed within 2 hours prior to enrollment.
- i Bleeding assessment is a clinical assessment of signs and symptoms of bleeding (eg, petechiae, bruises, epistaxis, hematuria, menorrhagia, gastrointestinal bleeding) performed by the Investigator.

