o First dose of the study intervention will be administered IV. A second dose is to be administered SC 4 to 6 hours after the IV dose on Day 1 followed by daily SC dose administration. A time window of \pm 1 hour is allowed for the daily SC study intervention administrations. Exception to this regimen: If a participant has received and tolerated a single dose of marketed caplacizumab intravenously (IV) for the presenting episode of iTTP within 4 hours prior to enrollment, the IV dose of study intervention at 0H will be skipped and the subcutaneous dose of caplacizumab due at 4-6H relative to the pre-study dose will be the first dose of study intervention. All subsequent doses will continue to follow the schedule as outlined in [Section 1.3.4](#) below. Please see [Section 1.3.4](#) below for details.

p For participants for whom TPE needs to be started only: TPE with plasma (eg, fresh frozen plasma, solvent detergent/viral-inactivated plasma, cryosupernatant) at 1 to 1.5 \times estimated plasma volume daily as of enrollment. See details in [Section 4.1](#).

q Recommend starting anti-CD20 antibody therapy (rituximab or biosimilar) once iTTP diagnosis is confirmed (ADAMTS13 level <10%) and is required if ADAMTS13 level remains <10%, 1 week after platelet count normalization or stop of TPE (if TPE was started).

s

1.3.3 Schedule of activities: Treatment and follow-up period (may include in-hospital & out-patient visits)

Study Period	Treatment Period (maximum 12 weeks)	Early Treatment Discontinuation Visit (\pm 3 days after last dose intake)	Follow-up Period ^l				
			FU Visit 7 days after last dosing (\pm 1 day)	Additional ^t FU Visit 14 days after last dosing (\pm 1 day)	Additional ^t FU Visit 21 days after last dosing (\pm 1 day)	FU visit 28 days after last dosing (\pm 1 day)	FU visit (EOS) 12 weeks after last dosing (\pm 3 days)
Study treatment administration							
IMP administration (daily) ^b	x						
Therapeutic plasma exchange (if needed) ^c	x						
Corticosteroids	x						
Anti-CD20 antibody therapy ^d	x						
eDiary (IMP administration info) ^e	x	x					
Safety and laboratory assessments							
Neurologic assessments ^f	x	x				x	x
GCS	x	x					x
Clinically significant TTP event	x	x	x	x	x	x	x
Bleeding assessment ^g	x	x	x	x	x	x	x
Physical examination	x	x	x	x	x	x	x
Vital signs ^h	x	x	x	x	x	x	x
12-lead ECG ⁱ	x	x				x	x
Adverse events	>						
Concomitant medication	>						
Clinical laboratory analyses ^j	x	x				x	x
Platelet count ^k	x	x	x	x	x	x	x

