Platelet count ^j	x ^g	x	x ^g	x	(x) ⁱ	x ^g	x	x	x ^g	x
Blood smear ^k	x ^g									
LDH ^l	x ^g	x	x ^g	x	(x) ⁱ	x ^g	x	x	x ^g	x
m	g					g			g	x

^a;GCS = Glasgow Coma Scale; IMP = investigational medicinal product; IV = intravenous; LDH = lactate dehydrogenase; PD = pharmacodynamics; PK = pharmacokinetics; RICO = ristocetin cofactor activity; SC = subcutaneous; TPE = therapeutic plasma exchange; TTP = thrombotic thrombocytopenic purpura; vWF = von Willebrand Factor.

^a Time (hour/minute) is expressed in reference to the first administration of IMP (T0H). In cases in which the participant has received and tolerated a dose of marketed caplacizumab for the presenting episode of iTPP within 4 hours prior to ICF signing, see footnote ^c below for interpretation of the time.

^b If TPE starts, blood draws during the TPE should be done only if possible.

- c If a participant has received and tolerated a dose of marketed caplacizumab IV for the presenting episode of iTTP within 4 hours prior to enrollment, the specific time of this dose should be documented, the IV dose of study intervention at 0H will be skipped and the subcutaneous dose of caplacizumab due at 4-6H after the pre-study dose, will be the first dose of study intervention. In these cases, all subsequent administrations of study intervention will continue to follow this schedule. The laboratory sampling schedule should remain unchanged (the time [hour/minute] for lab sampling is then expressed in reference to the time of enrollment).
- d First dose of the study intervention is to be administered IV. A second dose is to be administered SC 4 to 6 hours after the IV dose on Day 1 followed by daily SC dose administration. A time window of \pm 1 hour is allowed for the daily SC study intervention administrations. An exception to this is detailed in footnote [a](#).
- e For participants for whom TPE needs to be started only: TPE with plasma (eg, fresh frozen plasma, solvent detergent/viral-inactivated plasma, cryosupernatant) at 1 to $1.5 \times$ estimated plasma volume daily as of enrollment. See details in [Section 4.1](#).
- f Clinical laboratory analyses included hematology, coagulation parameters and clinical chemistry ([Section 10.2](#)).
- g Pre-cplacizumab dose.
- h Sample should be drawn before IMP administration and as close as possible to the IMP administration.
- i Optional assessments.

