- E 13. Participants who received an investigational drug, or device, other than caplacizumab, within 30 days of anticipated IMP administration or 5 half-lives of the previous investigational drug, whichever is longer. However, participants who have received any dose(s) of caplacizumab for the presenting episode of iTTP more than 4 hours before enrollment in Study EFC16521 are also excluded.

Diagnostic assessments

- E 14. Positive result on the Screening SARS-CoV-2 reverse transcription polymerase chain reaction (RT-PCR) test or on SARS-CoV-2 antigen test.

Other exclusions

- E 15. Sensitivity to any of the study interventions, or components thereof, or drug or other allergy that, in the opinion of the Investigator, contraindicates participation in the study.
- E 16. Individuals accommodated in an institution because of regulatory or legal order; prisoners or participants who are legally institutionalized.
- E 17. Participant not suitable for participation, whatever the reason, as judged by the Investigator, including medical or clinical conditions, or participants potentially at risk of noncompliance to study procedures.
- E 18. Participants are employees of the clinical study site or other individuals directly involved in the conduct of the study, or immediate family members of such individuals (in conjunction with section 1.61 of the ICH-GCP Ordinance E6).

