2 ANALYSIS POPULATIONS

The following populations for analyses are defined.

Table 3 - Populations for analyses

Population	Description
Screened	All participants who sign the informed consent form (ICF).
Enrolled	All participants from the screened population who met the eligibility criteria (ie, who are not screen failures). Participants who received caplacizumab and did not meet inclusion or met exclusion criteria are not enrolled, such as a participant with a confirmed alternate diagnosis.
Full Analysis Set (FAS)	All enrolled participants, who received at least 1 dose of the investigational medicinal product (IMP, ie, Caplacizumab). The FAS population will be used only for sensitivity analyses.
Modified ITT (mITT)	All enrolled participants who received at least 1 dose of IMP and with an evaluable primary endpoint. The mITT population will be the main efficacy analysis population. The primary endpoint is evaluable when the participant has an ADAMTS13 activity of <10% at baseline.
Safety	All enrolled participants who received at least 1 dose of IMP.
Pharmacokinetic (PK)	All enrolled and treated participants (safety population) with at least one post-baseline PK sample with adequate documentation of dosing and sampling dates and times.

Enrolled participants for whom it is unclear whether they took the IMP will be considered as exposed and will be included in the safety population.

To note that amended protocol 01 permits participants who have already received a dose of marketed caplacizumab for the presenting episode of iTTP within 4 hours prior to enrollment/ICF signing to enroll in the study. Consequently, participants exposed to a single dose of marketed caplacizumab within 4 hours prior to enrollment will be included in any analysis population.

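### The 4-hour limit on pre-study marketed caplacizumab runs back from enrollment in E 13 but from ICF signing in the footnote cited for the exception, and the SAP's Enrolled definition makes the difference count for a dosed patient

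*Protocol*

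**What the plan says.** The protocol lets a patient enter after a single IV dose of marketed caplacizumab for the presenting episode, subject to a 4-hour limit. The passages do not agree on the event from which the 4 hours are counted back.

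- **Protocol 5.2, E 13** excludes those who received "any dose(s) of caplacizumab for the presenting episode of iTTP more than 4 hours before enrollment in Study EFC16521 are also excluded".
- **Protocol 1.3.2, footnote o** applies the exception to a dose "for the presenting episode of iTTP within 4 hours prior to enrollment, the IV dose of study intervention at 0H will be skipped".
- **Protocol 1.3.4, footnote c** carries the dosing instruction and opens "If a participant has received and tolerated a dose of marketed caplacizumab IV for the presenting episode of iTTP within 4 hours prior to enrollment".
- **Protocol 1.3.4, footnote a** describes the same patients as dosed "for the presenting episode of iTPP within 4 hours prior to ICF signing", then refers on to footnote c for how to read the clock.
- **SAP section 2**, in the note below the population table, reports that the amended protocol admits patients dosed "within 4 hours prior to enrollment/ICF signing to enroll in the study". The next sentence, on inclusion in the analysis populations, uses enrollment alone.

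SAP 3.1 (baseline definition) and SAP 5.4 (time windows for daily values) also use enrollment.

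The Enrolled population in SAP section 2 is tied to meeting the eligibility criteria. It states that someone who received caplacizumab but met an exclusion criterion is not enrolled. FAS, mITT and Safety are all defined as subsets of Enrolled.

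**The concern.** Footnote a is more than a stray note. The synopsis, Table 3 in section 6.1, section 8 and footnote d of the flow chart all send the reader to it for the pre-dosed exception, so a site following those references meets the ICF anchor first.

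Two things are at stake. The first is who may enter after marketed caplacizumab, in a protocol whose section 5 forbids waivers. The second is which analysis sets hold a patient who was admitted and dosed on the ICF reading. If E 13 is then applied strictly, the SAP takes that patient out of the primary analysis set and also out of the Safety set. The FAS sensitivity analysis cannot bring the patient back, because FAS rests on the same Enrolled definition.

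**Working it through.** The plan gives no figure to reproduce beyond the 4-hour limit itself. The check compares the passages and does simple interval arithmetic.

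**Are the two anchors different times?** Yes. Protocol 10.1.3 requires consent before enrollment. Section 5.4 defines a screen failure as someone who consents and is not then enrolled. The screening table uses both anchors separately: the Glasgow Coma Scale is timed to enrollment, the ECG and troponin to ICF signing. On the possible gap, footnote a of 1.3.1 says "The Screening Period should not exceed more than 2 days" and also allows screening on the same day as baseline.

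**When do the rules disagree?** Let d be the hours from the marketed dose to ICF signing, and g the hours from signing to enrollment, with g ≥ 0.

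- ICF anchor: admitted if d ≤ 4.
- Enrollment anchor: admitted if d + g ≤ 4.
- Disagreement: d ≤ 4 < d + g, that is, d between 4 − g and 4.

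If d + g ≤ 4, then d ≤ 4 as well. No patient passes E 13 and fails footnote a, so the conflict is one-way.

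| d (assumed) | g (assumed) | d + g | Footnote a | E 13 |
|---|---|---|---|---|
| 1 h | 2 h | 3 h | fits | not excluded |
| 3 h | 2 h | 5 h | fits | excluded |
| 3.5 h | 2 h | 5.5 h | fits | excluded |
| 3.5 h | 3 h | 6.5 h | fits | excluded |

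The band of d on which the rules disagree is 1 hour wide if g = 1, 2 hours if g = 2, and the whole 4-hour window if g ≥ 4. Turning that width into a share of patients needs the distribution of d and the size of g. The documents give neither.

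**What happens to such a patient in the analysis?** The patient meets E 13, so under SAP section 2 is not Enrolled despite having been dosed, and is therefore outside FAS, mITT and Safety. On the ICF half of the SAP note, the same patient is one whom the protocol permits to enroll.

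**What could one reclassification do to the estimate?** As an illustration only, take 39 responders of 55 (70.9%), the whole number nearest the planning rate of 70%. Removing one responder gives 38/54 = 70.4%, a fall of about 0.5 points. Removing one non-responder gives 39/54 = 72.2%, a rise of about 1.3 points.

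**The case against.** The best reply is that there is only one eligibility rule. E 13 is the sole formal criterion on this point, and it is anchored to enrollment. Footnote a makes nobody eligible; it explains clock times and hands over to footnote c, which says enrollment. Footnote o, SAP 3.1, SAP 5.4 and the SAP's own sentence on inclusion in the analysis populations say the same. On that view the ambiguity comes down to one footnote and one slash in the SAP's summary of the protocol, and a careful site would apply E 13.

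Most of this stands, and it is why few participants are likely to be affected. The gap may also be short. The screening table accepts results from before consent for COVID-19 (72 hours), troponin (24 hours), ECG (4 hours), and platelets, smear and creatinine (24 hours), and same-day screening is allowed.

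The reply does not remove the contradiction. Footnote a is the place the protocol itself names for the exception, and the SAP sentence with both anchors is the one that speaks of permission to enroll.

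A reader might also infer that the ICF reading makes the dosing exception unworkable, since footnote c times the first study SC dose at 4 to 6 hours after the pre-study dose and section 6.2 limits study intervention to enrolled participants. The documents do not support that in general. At 5.5 hours the patient is still inside that window; it has closed before enrollment only when d + g exceeds 6 hours, as in the 6.5-hour row. This does not settle which anchor is right.

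**Conclusion.** The inconsistency is real, is in the current text and runs one way. It affects only patients given marketed caplacizumab no more than 4 hours before ICF signing and more than 4 hours before enrollment. The number is probably small. It cannot be estimated, because the documents state neither the consent-to-enrollment gap nor the share of participants pre-dosed.

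Two stronger readings are tempting. One is that sites will admit materially different patients; the documents do not show this, given that E 13 governs. The other is that each affected participant shifts the primary result by 1/55 = 1.8 points. That is one participant's share of the denominator. In the illustration above, removal moves the rate by 0.5 or 1.3 points, and nothing shows how many removals there would be.

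The point rests on population assignment. Whether a dosed patient's outcome and adverse events are analysed should not depend on which passage is read.

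**What to change.** Reconcile the passages to one anchor, chosen by the sponsor, and use the same words in E 13, in footnotes a and c of 1.3.4, in footnote o of 1.3.2 and in the SAP section 2 note. The smallest edit is footnote a and one SAP sentence, because the other passages already say enrollment. The opposite choice would mean editing those others, including SAP 3.1 and 5.4.

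The wording change alone does not say what happens to anyone already admitted on the other reading. Amend the Enrolled and Safety definitions in SAP section 2 so that a participant who received IMP on that basis is recorded as a protocol deviation, stays in the Safety set and, if baseline ADAMTS13 activity is below 10%, stays in the mITT set.

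The cost is one protocol footnote, one SAP sentence and one population definition. A few participants may become documented deviations.

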5.3 LIFESTYLE CONSIDERATIONS

5.3.1 Activity

Participants will abstain from strenuous exercise while on caplacizumab treatment and for 4 weeks after the last dose. Participants may participate in light recreational activities during studies (eg, watching television, reading).

5.4 SCREEN FAILURES

A screen failure occurs when a participant who consents to participate in the clinical study is not subsequently enrolled. A minimal set of screen failure information is required to ensure transparent reporting of screen failure participants to meet the Consolidated Standards of Reporting Trials (CONSORT) publishing requirements and to respond to queries from regulatory authorities. Minimal information includes demography, screen failure reasons, eligibility criteria, and any SAE.

Individuals who do not meet the criteria for participation in this study (screen failure) may not be rescreened during the same episode of iTPP. However, if the participant subsequently develops a relapse, he/she may be rescreened during this relapsed episode. Rescreened participants should be assigned a new participant number for every screening/rescreening event. Participants who are rescreened are required to sign a new ICF.

5.5 CRITERIA FOR TEMPORARILY DELAYING ENROLLMENT OR ADMINISTRATION OF STUDY INTERVENTION

During a regional or national emergency declared by a governmental agency, if the site is unable to adequately follow protocol mandated procedures, contingency measures are proposed in Appendix 9 ([Section 10.9](#): Contingency measures for a regional or national emergency that is declared by a governmental agency should be considered for enrollment or administration of study intervention.

6 STUDY INTERVENTION(S) AND CONCOMITANT THERAPY

Study intervention is defined as any investigational intervention(s), marketed product(s), placebo, or medical device(s) intended to be administered to a study participant according to the study protocol.

6.1 STUDY INTERVENTION(S) ADMINISTERED

After confirmation of eligibility to participate in the study, participants will receive caplacizumab in addition to IST.

Specific details pertaining to the IMP can be found in the pharmacy manual.

Table 3 - Study intervention(s) administered

Intervention label	Caplacizumab
Intervention name	Caplacizumab
Intervention description	Please see details below
Type	Biological/Vaccine
Dose formulation	Lyophilized powder for solution for injection.
Unit dose strength(s)	10 mg (or 11mg for US and Canada) - One vial contains 12.5 mg of caplacizumab and comprises an overfill to compensate for losses during reconstitution and liquid transfer
Dosage level(s)	Caplacizumab 10 mg (11 mg in US and Canada) IV for a single dose followed by caplacizumab 10 mg (11 mg in US and Canada) SC 4-6 hours after the IV dose (Day 1) (exceptions to this are detailed in Section 1.3.4 footnote ^a). This will be followed by caplacizumab 10 mg (11 mg in US and Canada) SC daily starting on Day 2 for a maximum treatment duration of 12 weeks for the presenting episode.
Route of administration	IV (first dose), SC (all subsequent doses)
Use	Experimental
IMP and NIMP	IMP
Packaging and labeling	The study medication is provided by the Sponsor in a kit containing 1 vial with caplacizumab lyophilized powder for solution, 1 pre-filled syringe with water for injection, 1 vial adapter, 1 SC safety needle and 2 alcohol swabs. The study medication will be labeled per country requirements
[Current/former name(s) or alias(es)]	ALX-0081/Cabiliivi

Table 4 - Study arm(s)

Arm title	Caplacizumab and immunosuppressive therapy without first-line therapeutic plasma exchange
Arm type	Experimental
Arm description	All participants will receive open label caplacizumab daily and immunosuppressive therapy (corticosteroid +/- anti-CD20 antibody therapy antibody [rituximab or biosimilar]) without first line TPE
Associated intervention labels	Caplacizumab, corticosteroid, anti-CD20 antibody therapy

Noninvestigational medicinal products (NIMPs)

For details of administration guidance please refer to [Section 4.1](#).

Immunosuppressive therapy: Corticosteroids:

- Formulation: Prednisone or Prednisolone
- Route(s) of administration: IV or oral
- Dose regimen: Prednisone or Prednisolone 1.0-1.5 mg/kg/day for 1 week and taper over 3 to 4 weeks based on institutional guidelines. The dose and duration of therapy may be adjusted as clinically indicated.

Anti-CD20 antibody therapy:

- Formulation: anti-CD20 antibody therapy (rituximab or biosimilar)
- Route(s) of administration: IV infusion (as per instructions on package insert)
- Dose regimen: 375 mg/m² IV infusion × 3 - 4 doses, once a week or as per institutional guidelines.

Note: Please see [Section 4.1](#) for additional details regarding anti-CD20 antibody therapy.

Therapeutic Plasma exchange (TPE), if needed:

- Plasma (fresh frozen plasma, solvent detergent/viral-inactivated plasma and cryosupernatant)
- Route(s) of administration: IV
- Dose regimen of TPE:
 - TPE with plasma at 1 to 1.5 × estimated plasma volume daily is recommended
 - TPE should be performed daily according to standard site practice and continued at least for 2 days after the platelet count normalization ($\geq 150 \times 10^9/L$).
 - Tapering of TPE after platelet count normalization, defined as reducing its frequency to less than once per day, is strongly discouraged and if considered, should be discussed with the Medical Monitor.

The IMP and NIMP may be supplied at the site or from the PI/site/Sponsor to the participant via a Sponsor-approved courier company where allowed by local regulations and agreed upon by the participant.

For a regional or national emergency declared by a governmental agency that results in travel restrictions, confinement, or restricted site access, contingency measures are included in Appendix 9 ([Section 10.9](#): Contingency measures for a regional or national emergency that is declared by a governmental agency.

